studies. The McGill Pain Questionnaire and Brief Pain Inventory are valid in many multilingual versions.

Luppanapornlarp et al, (2010)^[33] compared different magnitudes of continuous orthodontic force in order to determine the optimum orthodontic force. They measured Interleukin IL-1b levels in human gingival crevicular fluid (GCF), pain intensity, and the amount of tooth movement. This was carried out in the duration of canine retraction in 16 patients with Class I bimaxillary protrusion. Retraction of maxillary canines was performed using nickel–titanium coil springs on segmented arch-wires with continuous forces of 50g in one group and 150 g in the other group, while the lower canines were used as a control. It was found that IL-1b concentration in the 150 g group displayed the highest level at 24 hours and 2 months with significant differences compared with the control group. At 24 hours, the mean VAS score of pain intensity from the 150 g force was significantly greater than from the 50 g force.

Campos et al, (2013)^[34] conducted a study on twenty males to evaluate the relationship between the patient's motivation and the level of informed pain in the two stages of treatment. The questionnaire was divided into five categories including motivation towards treatment. Pain intensity was evaluated daily for fourteen days using a visual analog scale (VAS). The VAS was considered to have good reliability in recording motivation and pain intensity experienced by the patient.

6)3D model scanning and its reliability.

Santoro et al (2003)^[35] compared the reliability of measurements carried out on digital models and plaster models. Two independent examiners measured tooth size, overbite and overjet on both models belong to randomly selected pretreatment records of 76 patients. They concluded that, there was a significant difference in measurements tooth size and overbite readings with the

measurements on digital casts being smaller. On the other hand, there was no difference in the overjet measurements.

Asquith et al (2007)^[36] evaluated the accuracy and reproducibility of measurements made on digital models. They scanned ten study models using Arius3D Foundation System to produce 3D images. To measure reliability and reproducibility, two examiners measured eleven parameters, twice, on both digital models and study models. They concluded that digital models were a reliable mode of measurement and there was no longer a need to produce study models.

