- Crimbable hooks added to the arch wire (0.017"x0.025" Stainless steel) distal to the lateral incisor passing through the center of resistance of the anterior segment.
- A ligature wire extending between the canines and mini-screws will be used for proper anchorage control.

- Retraction will start on a 0.017"x0.025" Stainless steel wire with an elastomeric power chain (force applied will be 160 g) extending between the crimpable hooks and the mini-screws.
- The force will be measured by a force gauge and reactivated each visit to maintain force of retraction constant all over the retraction phase.

➤ **Follow up visits**

Patients will be asked to attend for follow up sessions every 4 weeks for:

- Evaluation of the mini implants stability.
- Replacement of the power chain to maintain a force of 160g.
- Reactivation of the T-loop by further distal activation and cinch back.

➤ **Criteria for discontinuing or modifying the allocated intervention:**

In cases of prolonged swelling or pain related to the miniscrew the patient will be given strict oral hygiene measures and may wait for three weeks before the beginning of retraction.

In cases of loose or broken miniscrews, the screw will be removed and replace the miniscrew after total resolution of the inflammation.

➤ **Post-retraction Questionnaire:**

The patients of both groups will be asked to fill in questionnaires regarding their experience with both techniques.

➤ **Retraction records**

The scanned dental models will assess the rate of retraction and molar anchorage loss achieved throughout the study.

➤ **Material Used**

- American Orthodontics Brackets, Roth prescription, Bidimensional slot size.
- American Orthodontics Elastomeric power chains
- American Orthodontics Elastomeric O-ties
- American Orthodontics Ligature wire.
- Jeil, Mini Screws, 8 mm length.
- American Orthodontics Arch wires.
- American Orthodontics Molar bands/tubes.

D] Outcomes

[figure not shown]
Primary outcome: is to monitor the rate of anterior segment retraction using both frictionless and friction methods.

Secondary outcomes is to monitor anchorage loss and pain, in association with each technique after retraction during anterior segment retraction,. All outcomes will be assessed as the difference between T_0 at the start of anterior segment retraction after full canine retraction and T_{final} after complete space closure.

E] Participant timeline:

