1. The principle investigator will screen the potential patients through careful clinical examination of patients at the orthodontic department, Faculty of Oral and Dental Medicine, Future University.

2. All recruited patients should fulfil the previously mentioned inclusion and exclusion criteria.
3. Every participant will be asked to sign an informed consent before the beginning of the study.
4. After patient's enrolment, each participant will be asked for pre-intervention records to ensure proper diagnosis.
5. The supervisor will randomly allocate the patients to one of the intervention groups.
6. Active intervention will begin after proper leveling and alignment of the upper and lower arches and canine retraction.
7. The principle investigator will take pre-retraction records for every participant. (T_0)
8. In Friction mechanics group, Power chain is used for anterior segment retraction while in Frictionless group, T-loop is used for retraction.
9. Each patient will come every 4 weeks for follow up visit, for appliance activation and uptake of impression for interim records.
10. After complete space closure, the principle investigator will take post-retraction records for each participant. (T_{final})
11. Every patient will fill up a questionnaire regarding his experience during treatment.
12. The principle investigator will continue the normal treatment and achieve proper finishing for every patient after the end of the study.

CONSORT flow chart of the flow of participants in the study.

E] Sample size calculation:

Our sample size calculation is based on a previous study comparing the effect of friction and frictionless mechanics. [14]

F] Recruitment strategy:

The principal investigator will recruit the patients from the clinic of Orthodontic department, Faculty of Oral and Dental Medicine- Future University.

Screening of patients will continue until the total number of participants for the study is collected.

II) Assignment of interventions:

A] Sequence generation:

The supervisor of the study will apply Computer generated random numbers to randomly assign patients to Group A (Friction) or B (Frictionless) using Microsoft Office Excel 2007 sheet. and will write the patient numbers in the first column, and will select function RAND() to generate the randomization number in the second column. These numbers will be sorted according to the randomization number so the first column numbers will be randomly distributed.

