B] Allocation concealment mechanism:

The supervisor of the study will write the randomization numbers of the patients in opaque white papers folded three times to form sealed envelopes and store it inside a box. Then will keep the Codes for randomization at the secretary office.

C] Implementation:

At time of intervention, the main operator will send the patient to the secretary office. Then, the assigned employee will open the box and ask the patient to select one envelope. the main operator will assign each participant for the

corresponding intervention either (friction or frictionless group) according to the list of codes of randomization.

Assignment to either intervention will occur before leveling and alignment stage.

D] Blinding:

Blinding of the operators: Blinding will not be possible for the operators during the application interventions and during the follow up visits. The principal operator is responsible for assigning subjects to interventions according to the concealed allocation, appliance activation at follow up visits, dental impressions and acquisition of dental casts.

Blinding of the outcome assessors: It is a single blinded study, the outcome assessors only will be blind. The patients name will be sealed from pre and post study models. Then two assessors will carry on, blindly and independently, the measurements and analysis of the study.

III) Data collection, management and analysis:

A] Data collection methods:

Primary outcome:

1. Retraction rate: to assess the antero-posterior movement of anterior teeth and first molars, the principle investigator will take study models for every participant monthly during the follow up visits. Then will digitize the models and identify the landmarks, reference lines and planes on the pre, interim and post-retraction digital dental models for measurements reading.

Secondary outcomes:

- 1. Anchorage loss:*** will be accessed by the principal investigator via scanned study models before and after the completion of retraction by identifying the landmarks, reference lines and planes, then will interpret the measurements in degrees and millimeters.
- 2. Pain:*** Each patient will fill a questionnaire regarding his treatment experience in a VAS scoring from 1-10. The questionnaire will include several questions related to oral hygiene, pain and discomfort experienced throughout the trial.

B] Data management:

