A] Data Monitoring: An independent Data Monitoring Committee (DMC) will monitor the results of the study. The Committee will include the trial's supervisors, who will periodically review the trial data and identify the need for any adjustments or modifications during the study.

B] Interim Analysis: no interim analysis will be performed during the study.

C] Harm: The main operator will document and report any harms or unwanted effects during the study intervention to the trial supervisors. Also any unpleasant

experience will be reported by the patient in the final questionnaire at the end of the retraction. The main operator will be responsible for the management of any adverse effects or unfavorable side effects resulting from the appliance.

D] Auditing: The supervisor will follow up and review the different interventions and resulting data. And he will periodically follow up the trial progress including recruitment of patients, allocation of participants to study groups; adherence to interventions and reporting of harms. A meeting with the senior supervisor will be set every 3 months to monitor the progress of the study and the need for any adjustments.

V) Ethics and dissemination:

A] Research Ethics Approval:

The Ethical committee in Future University, Egypt will review the protocol before they approve it. The research Ethics committee will evaluate the different interventions of the study to ensure its ethical validity and the potential benefits to the participants.

B] Protocol amendments:

The main investigator will be responsible to complete a formal amendment in case of any modifications or adjustments to protocol that may affect the conduct of the study, as changes in the study design or intervention procedures. The Orthodontics department, Faculty of Oral and Dental Medicine, Future University and the Ethics Committee will approve such amendment before proceeding in the study .

C] Consent:

The main investigator will be in charge for detailed explanation and elaboration of the different steps of the study interventions for each patient. Then will ask every participant to sign a written consent before they begin treatment. The consent will be written in Arabic.

D] Confidentiality:

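### Pain is defined as a change from T0 to Tfinal, but no T0 pain rating is scheduled, so that change cannot be computed

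*Combined protocol and SAP*

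**What the plan says.** Section D] Outcomes introduces pain with "Secondary outcomes is to monitor anchorage loss and pain, in association with each technique after retraction during anterior segment retraction". That wording puts the measurement both after and during retraction. The next sentence begins "All outcomes will be assessed as the difference between T_0 at the start of anterior segment retraction" and gives Tfinal, after complete space closure, as the other end of the difference. Pain is not exempted.

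The collection of pain is described in four other places:

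- Section III) A] Data collection methods, Pain: "Each patient will fill a questionnaire regarding his treatment experience in a VAS scoring from 1-10". No time point is given. The form covers "pain and discomfort experienced throughout the trial".
- Section C] Interventions has a heading "Post-retraction Questionnaire".
- Section E] Participant timeline, item 11: "Every patient will fill up a questionnaire regarding his experience during treatment". This follows item 10, the Tfinal records.
- Section IV) C] Harm: unpleasant "experience will be reported by the patient in the final questionnaire at the end of the retraction".

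The outcome table gives the pain tool as scoring sheets handed to patients, scored 1 to 10, without a schedule. Section D] Blinding blinds the outcome assessors only. Section C] Statistical Analysis, item 2, plans a paired t-test both between the groups and between pre- and post-treatment data within each group.

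**The concern.** A change score needs a rating at each end. The plan states a change for pain but schedules a rating at one end only. The outcome as defined, and any paired pre/post test of it, therefore has no data behind it. Ratings not taken at the start of or during retraction cannot be recovered later, so this has to be settled before patients reach that stage.

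What the schedule does deliver is one rating, from memory, of a long period, given by patients who know which appliance they had. The length of that period is tied to the primary outcome, because the faster a patient's space closes, the sooner she fills in the form. Pain is one of the two outcomes named under Secondary objectives, so readers will expect an interpretable comparison.

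**Working it through.** The plan gives no pain figure, sample size or pain effect to reproduce. The check is a count of scheduled ratings, followed by an illustration of recall length.

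**1. Scheduled pain ratings**

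| Time | What the plan schedules | Where | Pain ratings |
|---|---|---|---|
| T0, start of anterior retraction | Impressions, then scanned stone models | Acquisition of pre-intervention records | 0 |
| Each 4-weekly visit | Miniscrew stability, activation, impressions | Follow up visits; Participant timeline, item 9 | 0 |
| After Tfinal | Questionnaire with VAS | Post-retraction Questionnaire; Participant timeline, item 11; Harm | 1 |

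A T0 to Tfinal difference needs 2 ratings, one at each end. The schedule supplies 0 + 0 + 1 = 1, and the missing one is T0. The within-group paired test needs the same missing value.

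**2. Do the two definitions describe the same quantity?** They do not. The Outcomes section asks for a difference between two moments. The data collection section asks for a summary of a whole period. Adding a T0 rating alone would not reconcile them: T0 precedes the first activation of anterior retraction, and a whole-period rating minus a point rating is not the pain of retraction.

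**3. Recall length (illustration only)**

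Recall length = residual space / retraction rate, if the patient thinks back over anterior retraction alone.

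- Rate: 0.87 and 0.91 mm/month, the canine retraction rates with T-loops that the literature review reports. They are not incisor rates from this trial.
- Residual space: not stated in the documents. Assumed 3 to 7 mm.
- Shortest: 3 / 0.91 = 3.3 months. Longest: 7 / 0.87 = 8.0 months.
- With wider assumptions (2 to 7 mm, 0.5 to 1.5 mm/month): 2 / 1.5 = 1.3 months to 7 / 0.5 = 14 months.

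If patients also think back over levelling and canine retraction, the period is longer.

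**4. Dependence on arm.** With the same space s in both arms and rates r1 and r2, the recall lengths are s/r1 and s/r2. They are equal only if r1 = r2, which is the null hypothesis of the primary outcome. The documents give no rate for either arm of this trial, so no gap between arms is put forward here.

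**The case against.** The strongest reply is that the sentence about all outcomes is loose drafting. The data collection section treats the two secondary outcomes differently: anchorage loss is measured before and after retraction, while pain is asked about over the whole trial. Read that way, pain was always a post-retraction score, and comparing it between the randomised arms is legitimate. Much of this stands. It would be wrong to infer that pain cannot be analysed at all; only the change and its paired test are lost. The conflict remains, however, because the general sentence follows directly on the one naming pain and makes no exception.

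The outcome table's plural, scoring sheets, might hint at repeated collection. It may equally mean one sheet per patient. With no schedule attached, it does not supply a T0 rating.

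A reader might also infer that recall bias differs between the arms. The documents do not show this. Nothing in them links recall length to VAS score, and if patients think back over levelling and canine retraction too, the relative difference in recall shrinks.

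Nor does the cited finding that "At 24 hours, the mean VAS score of pain intensity from the 150 g force was significantly greater than from the 50 g force" settle when pain should be measured here. It contrasts two force levels, whereas this plan describes about 160 g in both arms. It shows only that a timed rating soon after loading has been used.

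The scale starting at 1 is a minor matter. Without anchors, 1 may mean no pain, and a constant shift cancels in a between-arm difference.

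**Conclusion.** The point holds in a limited form. As written, one of the two scores that define the pain outcome, T0, is never scheduled, so the T0 to Tfinal change in pain and any paired pre/post test of it cannot be computed. What remains is a between-arm comparison of a single retrospective rating by unblinded patients, over a period whose length depends on how fast the space closes. A difference in recall between the arms is a risk of unknown size and direction, not a demonstrated bias.

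The count rests on the written schedule being complete. If sheets are in fact handed out at other times, the plan needs to say so. Recall lasting months is an inference from repeated 4-weekly visits until closure and from the assumed spaces above; the plan states no retraction duration.

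The primary outcome is unaffected. Pain is also not one of only two secondary outcomes throughout the document, since the PICO section lists tip, torque and vertical position as well. The correction should be made, because it is cheap and the missing ratings cannot be obtained afterwards.

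**What to change.** 1. In D] Outcomes, exclude pain from the T0 to Tfinal sentence and define it as a between-arm comparison.
2. Give each patient a short VAS sheet at the start of retraction and at each existing 4-weekly visit. She completes it at a fixed time soon after that activation, for example 24 hours, and returns it at the next visit. Rating at the time avoids asking four weeks later about the first day.
3. State the anchors, including which value means no pain.
4. Compare the arms over a fixed number of early activations common to both, or with a repeated-measures model. A plain mean over all visits would average over a number of visits that depends on closure speed. The comparison should be for independent groups, since the paired t-test in the analysis section does not fit two parallel arms.
5. Keep the final questionnaire as a measure of overall experience.

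The cost is one short form per existing visit, some unreturned sheets to be handled as missing data, and the change of wording. No extra visits are needed. Patients would remain unblinded.

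If sheets at visits are not feasible, the minimum is to restate pain as a single post-retraction score compared between arms, with the recall period written into the question, and to make the Outcomes, data collection, timeline and analysis sections agree.

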- **Primary Outcome:** measuring the rate of anterior segment retraction for space closure when frictionless and friction mechanics were used.

Secondary Outcomes: measuring the changes in incisal position with regards to tip, torque and vertical position following

Outcome measure:

Outcome measure	Measure tool	Measure unit
1 ^{ry} Outcome	Assess the rate of anterior segment retraction	Digital scanned dental models. mm
2 ^{ry} Outcomes	1) Assess amount of anchorage loss.	Digital scanned dental models. mm
	2) Pain	Pain scoring sheets given to patients. VAS scoring from 1-10

B-Research question:

In orthodontic adolescent patients in need of 1st premolar extractions followed by anterior segment retraction, is there a difference, in terms of rate of anterior segment retraction, between friction and frictionless mechanics?

Objectives of the study

Research hypothesis:

The null hypothesis of this research is that there is no difference in rate of anterior segment retraction between friction and frictionless mechanics.

Primary objective:

Measuring the rate of anterior segment retraction using frictionless versus friction mechanics.

Secondary objectives:

Assess amount of anchorage loss and pain experienced.

Study design:

This is a randomized clinical trial with two arms parallel group and 1:1 allocation ratio. In one group, frictionless mechanics will be applied during anterior segment retraction while the other will receive friction mechanics during retraction to compare the results for differences in rate.

Materials and Methods

I)participants, interventions, and outcomes

A] Study Setting:

The study will be performed in the clinic of the Orthodontic Department at the Faculty of Oral and Dental Medicine, Future University. The recruited sample would be from the Egyptian urban and rural population.

B] Eligibility criteria:

- **Inclusion criteria:** for the participants include the following:
 1. Adolescent patients (females only).
 2. Patients requiring 1st premolars extraction followed by anterior segment retraction.
 3. Patients with fully erupted permanent teeth (not necessarily including the 3rd molar).
 4. Cases requiring maximum anchorage during anterior segment retraction.

- **Exclusion Criteria:** for the involved subjects included:
 1. Patients suffering from any systemic diseases interfering with tooth movement.
 2. Patients with extracted or missing permanent teeth. (except for third molars).
 3. Patients with badly decayed teeth.

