A colleague outside the research team will enter the data and organize it in excel sheets in the computer of the orthodontic department.

Data will include all photographs, models, radiographs and filled questionnaire.

C] Statistical Analysis:

- The principle investigator will be responsible for the extraction of the required data from the study models taken at every follow up visit. The data will be sent to a specialized statistician.
- The specialized statistician will be responsible for the statistical analysis of the study by:
 1. Presenting the data as mean, standard deviation (SD) and Standard error (SE) values.
 2. Using Paired t-test to compare between the friction and the frictionless group of retraction as well as to compare between the pre-and post -treatment data for each group.
 3. Using Kolmogorov Smirnov and Shapiro Wilk tests to determine the rate of anterior segment retraction.

4. Statistically evaluate the patient acceptance for both techniques.

- For this study, the specialized statistician will use IBM11 SPSS12 Statistics Version 20 for Windows to perform the required statistics.
- The significance level will be $P \leq 0.05$. Highly significant variables are detected when P value is less than 0.01.

Assessors Reliability:

- To achieve high reliability for measurements, the supervisor will choose a well-experienced inter-examiner during the study.
- A training session will be provided for the examiners to ensure standard measurements techniques.
- Each examiner will complete the measurements on a model and will repeat the procedure after one week to assess the intra- and inter-examiner reliability.
- The supervisor will compare the measurements of the two assessors for disagreement with a difference of more than one millimeter.
- The supervisor will evaluate the amount of variation in measurements among and between examiners to test the performance of each assessor.
- The examiner with less reliability will receive additional training but will be replaced during the study.
- The specialized statistician will calibrate the intra and inter-examiner reliability for the measurements of the study by Inter-observer and intra-observer reliability was assessed using $P \leq 0.05$.

IV) Method Monitoring:

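### The plan compares two independent randomised arms with a paired t-test, so the primary P value depends on arbitrary row order and degrees of freedom (and patients, if arms are unequal) are lost

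*Combined protocol and SAP*

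**What the plan says.** The Study design section reads: "This is a randomized clinical trial with two arms parallel group and 1:1 allocation ratio". Under Sequence generation, the supervisor will "randomly assign patients to Group A (Friction) or B (Frictionless) using Microsoft Office Excel 2007 sheet", so the unit randomised is the patient, not a side or a quadrant. Under Implementation, "the assigned employee will open the box and ask the patient to select one envelope", which is an individual draw with no matching step. The Participant timeline gives one technique to each group: "In Friction mechanics group, Power chain is used for anterior segment retraction while in Frictionless group, T-loop is used for retraction".

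Item 2 of the Statistical Analysis section then specifies "Using Paired t-test to compare between the friction and the frictionless group of retraction", and the sentence goes on: "as well as to compare between the pre-and post -treatment data for each group". The paired test is therefore given two separate jobs, one between the arms and one within each arm.

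No independent-samples test is named anywhere. Item 3 names only normality tests. Item 4, on patient acceptance, names no test. The Sample size calculation section refers to a previous study and gives no number of patients, power, standard deviation or difference.

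**The concern.** A paired t-test analyses the differences within pairs. It needs a reason, fixed before the data are seen, why a given value in one arm belongs with a given value in the other. Here there is none. The software would pair row 1 with row 1, row 2 with row 2, and so on, and row position carries no information about the patients.

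Three things follow:

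- The primary P value is not determined by the data. Two analysts with the same measurements in a different order would report different results.
- The test has n − 1 degrees of freedom instead of 2n − 2.
- If the arms end unequal, each unpaired patient is left out, so a dropout in one arm also removes a valid patient from the other.

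As the only named between-group test, it would decide the trial's null hypothesis on retraction rate.

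**Working it through.** **Inputs from the documents.** Two parallel arms, 1:1, patients randomised individually, one technique each; significance level 0.05. There is no planned figure to reproduce.

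**Assumptions.** Two-sided test; 8 to 30 patients per arm; normal data with equal SD.

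**1. Degrees of freedom and power.** With n per arm and standardised difference d, both tests have noncentrality d × √(n/2) when the pairing is arbitrary. Only the degrees of freedom differ: 2n − 2 (independent) against n − 1 (paired). For each n, d is set to give the independent test 80% power.

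| n per arm | df, independent / paired | critical t, independent / paired | d | paired power |
|---|---|---|---|---|
| 8 | 14 / 7 | 2.145 / 2.365 | 1.51 | 73% |
| 10 | 18 / 9 | 2.101 / 2.262 | 1.33 | 75% |
| 12 | 22 / 11 | 2.074 / 2.201 | 1.20 | 76% |
| 15 | 28 / 14 | 2.048 / 2.145 | 1.06 | 77% |
| 20 | 38 / 19 | 2.024 / 2.093 | 0.91 | 78% |
| 30 | 58 / 29 | 2.002 / 2.045 | 0.74 | 79% |

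**2. Dependence on row order.** Re-ordering rows leaves both arm means unchanged but alters the correlation r between the columns. With equal arm SDs, t(paired) = t(independent) / √(1 − r).

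Take 12 per arm and data with independent-test P = 0.050, so t = 2.074. The paired test is significant when 2.074 / √(1 − r) ≥ 2.201, that is, 1 − r ≤ (2.074 / 2.201)² = 0.888, or r ≥ 0.112. Over random orders r has mean 0 and SD 1/√11 = 0.302. The chance of r ≥ 0.112 is therefore about that of a standard normal value above 0.112 / 0.302 = 0.37, or 36%.

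Simulated re-orderings agree: about 36% of orders give P ≤ 0.05, and the central 95% of paired P values runs from about 0.01 to 0.13. At 10, 15 and 20 per arm the ranges are 0.007–0.134, 0.011–0.118 and 0.014–0.108, with 35%, 37% and 40% of orders significant. If the independent-test P is 0.086 (12 per arm), about 13–15% of orders still give P ≤ 0.05.

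**3. Type I error.** With rows in an order unrelated to outcome, simulated type I error is 4.97%, 5.02% and 5.05% at 10, 15 and 20 per arm. If each arm were sorted by outcome before pairing, it would be 48%, 56% and 60%.

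**4. Unequal arms.** Assume 12 and 10 patients and d = 1.2 (for example a difference of 0.48 mm/month with SD 0.40; both values are assumptions).

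- Independent test, all 22 patients: noncentrality 1.2 / √(1/12 + 1/10) = 2.80, df 20, power 76%.
- Independent test after discarding two patients: noncentrality 1.2 × √5 = 2.68, df 18, power 72%.
- Paired test on 10 pairs: noncentrality 2.68, df 9, power 67%.

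The 9-point loss is thus about 4 points from lost patients and 5 from lost degrees of freedom.

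If randomisation were unrestricted (an assumption, as the plan does not say how the sorted list is split), the arms would be unequal with probability 82%, 86% and 87.5% at totals of 20, 30 and 40. On average 3.5, 4.3 and 5.0 patients would be unpaired.

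**The case against.** The strongest defence is that the practical damage may be small. If the rows are in an order unrelated to outcome, type I error stays at about 5%. The power loss is only 1 to 2 points at 20 to 30 per arm. With equal arms, as the 1:1 ratio intends, no patient is dropped. A fixed spreadsheet also gives the same paired P each time it is analysed. All of this is true. The power loss alone would not justify a mandatory change, and the loss of patients must be stated as conditional on unequal arms.

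It does not rescue the test. That a fixed spreadsheet returns a fixed answer does not make the answer meaningful, because another equally valid order returns a different one. The plan sets no rule for row order, and the reassurance on type I error fails if the order is related to outcome.

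It could also be said that the statistician would quietly use the right test. That would be an unrecorded change to the primary analysis, when the plan has its own amendment procedure.

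Nor can item 2 be read as covering only the pre/post comparison, since it lists the two uses separately. Split-mouth designs appear in the literature review, but only as descriptions of other studies.

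**Conclusion.** The concern holds, and the text must be corrected before analysis. The named test for the primary comparison does not match the design, and its P value would depend on row order. The mismatch follows from the documents alone and needs no assumption about size.

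The numerical consequences rest on assumed sample sizes, differences and SDs. For a borderline result at 12 per arm, row order alone decides significance, with about 36% of orders on one side and 64% on the other. Power drops by about 7 points at 8 per arm, 4 at 12 and 1 at 30. In the 12 v 10 example it drops by 9 points. The paired test remains suitable for pre/post change within an arm.

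**What to change.** Reword item 2 of the Statistical Analysis section along these lines: *The retraction rate will be compared between the groups with an independent two-sample (Welch) t-test, reporting the mean difference with its 95% confidence interval. The paired t-test will be used only to describe pre/post change within each group.*

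The essential step is to name an independent-samples test. Welch rather than the pooled version is a conventional choice. If Mann-Whitney is kept as an alternative for clearly non-normal data, the criterion for switching should be written down beforehand.

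Anchorage loss and pain also need independent-samples comparisons. Pain is a 1–10 score, so the choice between a t-test and a rank test should be stated for it separately.

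The cost is one sentence, made through the plan's amendment route, with no extra patients or data.
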